7.4. Dosage Modification

7.4.1. Study Drugs

No adjustment in study drug doses will be allowed. Details about dose administration of tirzepatide during the study are described in Sections [7.2.1](#) and [8.1.2](#).

7.4.2. Initiation of New Antihyperglycemic Medication

The introduction of new antihyperglycemic medication is expected during the study only in the following situations:

- As an antihyperglycemic intervention for severe, persistent hyperglycemia ("rescue therapy"), as defined in Section [9.2.2.2](#).
- In those patients who require permanent discontinuation of study drug, but remain in the study (Section [8.1.1](#))
- During the safety follow-up period (between Visit 14 [Week 40] or ET and Visit 801), only if the patient needs additional glycemic control as outlined in Section [5.1](#) under study Period III (safety follow-up period) discussion.

If a new antihyperglycemic medication is introduced, metformin will be the first choice of therapy unless contraindicated. Glucagon-like peptide-1 receptor agonists, DPP-4 inhibitors, and pramlintide are not allowed. Initiation of insulin as first rescue intervention for hyperglycemia should be reserved for patients with severe, persistent hyperglycemia with an average FSG ≥ 300 mg/dL (≥ 16.7 mmol/L) or in other clinical situations where the investigator believes more rapid glycemic control is warranted.

7.5. Preparation/Handling/Storage/Accountability

The investigator or his or her designee is responsible for the following:

- confirming appropriate temperature conditions have been maintained during transit for all study treatment received and any discrepancies are reported and resolved before use of the study treatment.

- ensuring that only participants enrolled in the study may receive study treatment and only authorized site staff may supply or administer study treatment. All study treatments must be stored in a secure, environmentally controlled, and monitored (manual or automated) area in accordance with the labeled storage conditions with access limited to the investigator and authorized site staff.
- the investigator, institution, or the head of the medical institution (where applicable) is responsible for study treatment accountability, reconciliation, and record maintenance (such as receipt, reconciliation, and final disposition records).

The study site must store the study drug in a locked and secure environment. Please refer to the study drug label for specific storage conditions. Patients will receive insulated bags with cooling gel packs for use in transporting the study drug carton from the site to home.

Study site staff must regularly assess whether the patient is correctly administering the assigned study drug and storing the study drug according to the provided instructions.

7.6. Treatment Compliance

Study drug compliance will be determined by the following:

- Study drug administration data will be recorded by the patient and reviewed by the investigator at each study visit.
- The patients will be instructed to return any unused study drug and/or empty cartons at the next visit to the study site for the purpose of performing drug accountability.

In the 3 tirzepatide treatment groups, as well as the placebo group, treatment compliance for each visit interval is defined as taking at least 75% of the required doses of study drug. Similarly, a patient will be considered significantly noncompliant if he or she is judged by the investigator to have intentionally or repeatedly taken more than the prescribed amount of medication.

In addition to the assessment of a patient's compliance with the study drug administration, other aspects of compliance with the study treatments will be assessed at each visit based on the patient's adherence to the visit schedule, completion of study diaries, the results of home BG monitoring, and any other parameters the investigator considers necessary.

Patients considered to be poorly compliant with their medication and/or the study procedures will receive additional training and instruction, as required, and will be reminded of the importance of complying with the protocol.

7.7. Concomitant Therapy

Patients will be permitted to use concomitant medications that they require during the study, except certain medications that may interfere with the assessment of efficacy and safety characteristics of the study treatments.

Investigative site staff will inform patients that they must consult with the investigator or a designated site staff member upon being prescribed any new medications during the study. This

may not be possible when initiated for treatment of medical emergencies, in which case, the patient will inform the investigator or a designated site staff member as soon as possible. Any additional medication initiated during the course of the study (including OTC drugs, such as paracetamol or aspirin) must be documented, and the name of the drug and the date(s) of administration must be recorded on the “Concomitant Medications” section of the eCRF.

Antihyperglycemic medications other than study drugs are not allowed at any time during the study except as allowed for those patients who require permanent discontinuation of study drug, but remain in the study, rescue therapy after randomization due to severe, persistent hyperglycemia; or during the safety follow-up period (see Section 7.4.2). Short-term insulin use for up to 14 days is allowed for certain clinical situations (for example, elective surgery, during hospitalization, hyperosmolar states) and must be differentiated from insulin use as rescue therapy when reported in the eCRF.

All nonstudy medications will be recorded on the eCRF at all visits.

Nonstudy medications taken by patients who are screened but not randomized will not be reported to Lilly unless an SAE or AE occurs that the investigator believes may have been caused by a study procedure.

7.8. Treatment after the End of the Study

7.8.1. Treatment after Study Completion

Study completion will occur after all patients complete the follow-up visit. Investigators will continue to follow Schedule of Activities (Section 2) for all patients until notified by Lilly that study completion has occurred.

Tirzepatide will not be made available after conclusion of the study to patients.

7.8.2. Special Treatment Considerations

This section provides guidance on management of episodes of hypoglycemic events; severe, persistent hyperglycemia during the treatment period; patients who permanently discontinue study drug prior to Visit 14; and patients with GI symptoms. For effective implementation of measures described here, it is important that patients, and their caregivers, if applicable, be well educated about the signs and symptoms of hyperglycemia (for example, severe thirst, dry mouth, frequent micturition, or dry skin) and hypoglycemia (for example, intense hunger, sweating, tremor, restlessness, irritability, depression, headaches, disturbed sleep, or transient neurological disorders). Patients should be instructed to contact the investigative site in the event of severe, persistent hyperglycemia or severe hypoglycemia between study visits or in the event when a patient intends to permanently discontinue study drug.

7.8.2.1. Standards of Medical Care

Investigators and other study team members are expected to treat patients according to the nationally established standards of care for diabetes management in respective participating countries, except where that treatment would be in conflict with the protocol-provided treatment

requirements. If there are no local standards of care for diabetes, the investigators should follow current published standards of care from the American Diabetes Association and the European Association for Study of Diabetes (Davies et al. 2018) during their patients' participation in this study.

7.8.2.2. Management of Hypoglycemia Risk

In this study, increased risk of hypoglycemia is defined as having a single episode of severe hypoglycemia or having more than 1 episode of documented symptomatic hypoglycemia within a 1-week period at any time during the treatment period. In cases where a patient experiences hypoglycemia as described above, to confirm the increased risk, the study sites must ensure that the patient has been fully compliant with the assigned therapeutic regimen and also that there is no evidence of other possible causes of hypoglycemia (for example, omission of meal, unexpected increase in exercise). If the patients fulfill the definition of increased risk of hypoglycemia, the investigator should discontinue the patient from study treatment and follow the guidance for management of patients to permanently discontinue the study drugs as outlined in Section 8.1.1.

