The Schedule of Activities described below should be followed for all patients enrolled in Study GPGK. However, for those patients whose participation in this study is affected by severe acute respiratory syndrome coronavirus 2 (SARS-CoV-2), the virus that causes the novel Coronavirus Disease 2019 (COVID-19), please refer to [Appendix 8](#) for additional instructions.

Table GPGK.1. Schedule of Activities

	Study Period I		Study Period II													Study Period III
	Screening/ Lead in		Treatment Period													
Visit	1	2	3 ^a	4	5	6	7	8	9	10	11	12	13	14	ET ^b	801
Week of Treatment	-3	-2	0	4	7	8	12	15	16	20	23	24	32	40		4 weeks post end of tx
Allowable Deviation (days) ^c		±3	±7	±3	-	±3	±3	-	±3	±3	-	±3	±7	±7		±7
Fasting Visit ^d			X	X		X	X		X	X		X	X	X	X	
PK specific Visit ^e					X			X			X					
Informed consent	X															
Randomization			X													
Clinical Assessments																
Medical history ^f	X															
Physical	X														X	X
Height	X															
Weight ^g	X		X	X		X	X		X	X		X	X	X	X	
Waist circumference			X	X		X	X		X	X		X	X	X	X	
Electrocardiogram ^h			X												X	X
Vital signs (2 sitting BP and HR) ⁱ	X		X	X	X	X	X	X	X	X	X	X	X	X	X	
Dilated fundoscopic Examination ^j		X														
Adverse events	X	X	X	X	X	X	X	X	X	X	X	X	X	X	X	
Concomitant medications	X	X	X	X	X	X	X	X	X	X	X	X	X	X	X	
Review hypoglycemic events collected in the diaries			X	X		X	X		X	X		X	X	X	X	

	Study Period I		Study Period II														Study Period III
	Screening/ Lead in		Treatment Period														Safety F/U
Visit	1	2	3 ^a	4	5	6	7	8	9	10	11	12	13	14	ET ^b	801	
Week of Treatment	-3	-2	0	4	7	8	12	15	16	20	23	24	32	40		4 weeks post end of tx	
Allowable Deviation (days) ^c		±3	±7	±3	-	±3	±3	-	±3	±3	-	±3	±7	±7		±7	
Fasting Visit ^d			X	X		X	X		X	X		X	X	X	X		
PK specific Visit ^e				X			X			X							
Diabetes education ^{k,l}		X															
BG meter, SMBG training ^m		X															
Dispense BG meter/supplies as needed		X	X	X		X	X		X	X		X	X	X	X		
Study drug injection training with demo device ^l			X														
Hand out diaries, instruct in use ^l		X	X											X	X		
Remind patients about 7-point SMBG ^m		X				X							X	X	X		
Review 7-point SMBG values collected in the diaries			X				X						X			X	

	Study Period I		Study Period II													Study Period III
	Screening/ Lead in		Treatment Period													Safety F/U
Visit	1	2	3 ^a	4	5	6	7	8	9	10	11	12	13	14	ET ^b	801

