At Visit 2, the screening laboratory results will be reviewed. For those patients meeting all other eligibility requirements, a dilated fundoscopic examination, performed by an ophthalmologist or optometrist, must be completed between Visit 2 and Visit 3 to ensure that patients with proliferative diabetic retinopathy, diabetic maculopathy, or nonproliferative diabetic retinopathy who require acute treatment, are identified and excluded. Additionally, at Visit 2, patients and their caregiver(s), if applicable, will receive a glucometer and training on how to perform self-monitoring of blood glucose (SMBG). Patients will be asked to monitor fasting blood glucose (FBG) 4 times a week and two 7-point SMBG profiles done on 2 nonconsecutive days in the 2-week period prior to Visit 3 (randomization), Visit 7 (Week 12), Visit 14 (Week 40), and Visit 801 (Week 44). Patients will be provided diaries and will be trained as appropriate to record blood glucose (BG) values and hypoglycemic events. During this period, patients will also be trained on disease management (symptoms of hypoglycemia and hyperglycemia) and study procedures; this training can be repeated at subsequent visits as deemed appropriate. Patients should monitor BG any time a hypoglycemic event is suspected. During the lead-in period, patients should continue their diet and exercise routine and must not add any OAMs in order to allow reliable assessment of HbA1c at baseline (Visit 3).

Study Period II (40-week treatment period)*Randomization (Visit 3)*

At Visit 3, eligible patients will perform all required baseline study procedures (including the collection of all baseline laboratory measures and electrocardiogram [ECG]) prior to randomization and prior to taking the first dose of study drug except for PK sample collection which will be collected anytime on the same day after administration at the site (see Section 2). Patient should arrive to the clinic in the fasting state; the fasting state should have lasted at least 8 hours. The questionnaires (European Quality of Life-Dimensions [EQ-5D-5L], Ability to Perform Physical Activities of Daily Living [APPADL], Impact of Weight on Self-Perception [IW-SP]) should be completed before any other study procedures if the patient is not adversely affected by the fasting condition or completed after the patient has sufficiently recovered from the preceding visit procedures.

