9.2.2.11. Acute Renal Events

Renal safety will be assessed based on repeated renal functional assessment as well as assessment of AEs suggestive of acute or worsening of chronic renal failure. Gastrointestinal AEs have been reported with tirzepatide, including nausea, diarrhea, and vomiting. These are

consistent with other GLP-1 receptor agonists (Aroda and Ratner 2011). The events may lead to dehydration, which could cause a deterioration in renal function, including acute renal failure. Patients should be advised to notify investigators in case of severe nausea, frequent vomiting, or symptoms of dehydration.

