Appendix 3.2.1. Data Capture System

The investigator is responsible for ensuring the accuracy, completeness, legibility, and timeliness of the data reported to the sponsor.

An electronic data capture system (EDC) will be used in this study for the collection of CRF data. The investigator maintains a separate source for the data entered by the investigator or designee into the sponsor-provided EDC system. The investigator is responsible for the identification of any data to be considered source and for the confirmation that data reported are accurate and complete by signing the CRF.

Additionally, clinical outcome assessment data (scales, self-reported diary data) will be collected by the patient/investigator site personnel, via a paper source document, and will be transcribed by the investigator site personnel into the EDC system.

Data collected via the sponsor-provided data capture system(s) will be stored at third parties. The investigator will have continuous access to the data during the study and until decommissioning of the data capture systems. Prior to decommissioning, the investigator will receive an archival copy of pertinent data for retention.

Data managed by a central vendor, such as laboratory test data, will be stored electronically in the central vendor's database system, and electronic transfers will be provided to the investigator for review and retention. Data will subsequently be transferred from the central vendor to the Lilly data warehouse.

Data from complaint forms submitted to Lilly will be encoded and stored in the global product complaint management system.

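### The between-visit contact instruction omits one of the two hypoglycemia triggers for stopping study drug, so a site may learn of it only at the next diary review

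*Protocol*

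**What the plan says.** Section 7.8.2.2 of the protocol defines increased hypoglycemia risk by either of two triggers: a single severe episode, or "having more than 1 episode of documented symptomatic hypoglycemia within a 1-week period at any time during the treatment period". The same steps follow both. First comes confirmation: "to confirm the increased risk, the study sites must ensure that the patient has been fully compliant with the assigned therapeutic regimen", and other explanations such as a skipped meal or unusual exercise must be excluded. If the definition is then fulfilled, "the investigator should discontinue the patient from study treatment". Section 8.1.1 lists this among the reasons for permanent discontinuation.

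Section 7.8.2 tells patients when to call: "Patients should be instructed to contact the investigative site in the event of severe, persistent hyperglycemia or severe hypoglycemia between study visits". The same sentence adds the case of a patient who intends to stop study drug for good. It does not mention repeated symptomatic episodes.

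The other relevant provisions concern measuring and recording. Section 5.1 says "Patients should monitor BG any time a hypoglycemic event is suspected" and has patients record glucose values and events in a diary. Section 9.2.2.1 has site staff enter hypoglycemia information in the eCRF at each visit. Appendix 3.2.1 says that "clinical outcome assessment data (scales, self-reported diary data) will be collected by the patient/investigator site personnel, via a paper source document". The Schedule of Activities row "Review hypoglycemic events collected in the diaries" is marked at Visits 3, 4, 6, 7, 9, 10, 12, 13 and 14 and at early termination.

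**The concern.** The second trigger is counted over one week and can end in permanent discontinuation, yet a patient who follows the contact instruction exactly has no reason to call when it is met. Diaries are on paper, and no remote alert is described. The site can therefore start the assessment required by Section 7.8.2.2 only when it next sees the diary or happens to hear of the episodes another way.

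What is at stake is prompt assessment. The patient goes on injecting drug already dispensed, and the cause of the episodes becomes harder to establish as time passes, particularly whether a meal was missed or exercise was unusual. The wait is longest after Week 24, when every arm has reached its maintenance dose.

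**Working it through.** The documents give no figure for this delay, so there is none to reproduce. The check has two parts.

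**1. Is the second trigger covered anywhere else?**

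| Provision | What it asks for | Covers repeated symptomatic episodes between visits? |
|---|---|---|
| 7.8.2 | Contact for severe, persistent hyperglycemia, severe hypoglycemia, or intent to stop drug | No |
| 5.1 | Measure glucose, keep a diary | No; recording only |
| 9.2.2.1 | Site enters hypoglycemia data at each visit | No; at visits only |
| 7.8.2.4 | Notify the site promptly on stopping drug | No; different event |
| 9.2.2.11 | "Patients should be advised to notify investigators in case of severe nausea, frequent vomiting, or symptoms of dehydration" | No; different symptoms |

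The last two rows show that the protocol does write notification instructions where it wants them.

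**2. How long can the wait be?**

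Inputs from the Schedule of Activities: diary reviews at Weeks 0, 4, 8, 12, 16, 20, 24, 32 and 40; windows of ±3 days at Weeks 4 to 24 and ±7 days at Weeks 32 and 40. Visit dates are counted from the randomization visit, so Week 0 contributes no window.

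Nominal gap = (later week − earlier week) × 7 days.
Longest gap = nominal gap + earlier visit's minus-window + later visit's plus-window.

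| Interval | Nominal | Longest with windows |
|---|---|---|
| Weeks 0–4 | 4 × 7 = 28 days | 28 + 0 + 3 = 31 days |
| Each 4-week interval from Week 4 to Week 24 | 28 days | 28 + 3 + 3 = 34 days |
| Weeks 24–32 | 8 × 7 = 56 days | 56 + 3 + 7 = 66 days |
| Weeks 32–40 | 56 days | 56 + 7 + 7 = 70 days |

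**Pharmacokinetic visits.** Weeks 7, 15 and 23 are also site contacts. Adverse events are collected there, although no hypoglycemia diary review is scheduled. Counting them as opportunities to detect the trigger splits three of the six early intervals into 3 weeks and 1 week (4–7–8, 12–15–16, 20–23–24). Weeks 0–4, 8–12 and 16–20 contain no such visit and stay at 4 weeks. No visit of any kind falls between Weeks 24 and 32 or between Weeks 32 and 40. The nominal maxima of 4 and 8 weeks are therefore unchanged.

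**The case against.** The strongest reply is that this is a graded design: urgent events prompt a call, and milder ones wait for the diary. Two symptomatic readings at or below 70 mg/dL meet the trigger, and that is the protocol's Level 1 alert value. Any episode with severe cognitive impairment needing another person's help is Level 3 and already prompts contact. Patients are trained to recognize and treat hypoglycemia. Tirzepatide is given here as monotherapy, and Section 3.2 reports no severe hypoglycemia in the earlier work it describes. This limits the likely harm. It does not explain why two triggers with the same consequence have different reporting routes, or why a rule counted over one week should wait up to eight. Nor is a pattern too much to ask of patients. The same sentence already asks them to report severe, persistent hyperglycemia, which Section 7.8.2.3 defines mainly by readings over two consecutive weeks.

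Second, Section 7.8.2 stresses that patients be well educated about hypoglycemia, and training, diary or consent materials may tell them when to call. Those materials are not available here, so the finding is about the protocol text only.

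Third, before Week 24 the pharmacokinetic visits and data entry at each visit give further chances of detection. That narrows the early gap, but attendance at those visits depends on the sampling window assigned to the patient, and three early intervals have none.

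A reader might go further in four ways that the documents do not support:
- **A count of extra doses or an average wait.** These need an assumption about when in an interval the trigger occurs, and the documents give no basis for one.
- **A still longer final gap when Visit 14 moves to Week 44 under Appendix 8.** That extension requires additional drug and, as local rules demand, additional consent, so a period without contact is doubtful.
- **That every patient meeting the trigger is wrongly kept on drug.** Some will have another cause and will rightly continue. Doses and episodes are recorded, so a late check is still possible.
- **That severe hypoglycemia is affected.** It is named in the contact instruction.

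**Conclusion.** The gap in the text is real and its consequence is minor. Two triggers lead to the same assessment and possible discontinuation, but patients are told to report only one of them between visits. For the other, the site may not learn of the episodes until the next diary review: nominally up to 4 weeks before Week 24 and up to 8 weeks after it, or up to 34 days and 66 to 70 days at the edges of the visit windows. Weekly dosing continues meanwhile.

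This rests on three conditions: the patient does not volunteer the episodes, they do not surface at a pharmacokinetic visit, and materials outside the protocol do not already close the gap. The documents give no event rate, so the number of patients affected cannot be estimated. It is probably small, and the omitted events are mostly non-severe. No endpoint, power calculation or type 1 error rate is affected.

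**What to change.** In Section 7.8.2, extend the list of reasons for contacting the site between visits to read: *severe, persistent hyperglycemia, severe hypoglycemia, or more than 1 episode of symptomatic hypoglycemia with PG ≤70 mg/dL (3.9 mmol/L) within 1 week*. The threshold is the one in Section 9.2.2.1 and also takes in Level 2 readings. Add one matching line to patient training.

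The site can then make the Section 7.8.2.2 assessment when the pattern occurs. Whether to interrupt dosing in the meantime stays with the investigator under Section 8.1.2. The cost is a few extra patient calls; no visit, assessment or dosing rule changes.
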